6.8. SOFTWARE VERSION

Apart for the supplementary analysis of the primary endpoint exploring the dose response relationship (generalized MCP-Mod using the DoseFinding package, version 0.9-16) which will use R software version 3.5.3 or higher (R Foundation for Statistical Computing, Vienna, Austria), all other analyses will be conducted using Statistical Analysis System (SAS[®]) version 9.4 or higher (SAS Institute, Inc., Cary, North Carolina).

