16.1.5.3. Analysis of dose-response

A supplementary analysis of the primary efficacy of SEP-4199 will be conducted on the ITT population to explore the dose response relationship using the generalized Multiple Comparison Procedure – Modeling (gMCP-Mod) methodology (Pinheiro 2014).

The gMCP-Mod approach to dose response will be implemented using R software, in particular the DoseFinding package ([APPENDIX 3](#)).

First, to obtain estimates of the dose response, an MMRM model on the ITT population with factors for treatment dose level, region, week, and baseline MADRS score as a continuous covariate will be used to model the change from baseline in MADRS score over time from the placebo and SEP-4199 groups. The LS mean of change from baseline in the MADRS total score at Week 6 for each SEP-4199 group and placebo and the corresponding variance-covariance matrix will be obtained from the model.

Next, the gMCP-Mod approach will use the estimates obtained from the MMRM model to analyze the dose response relationship at Week 6. The following set of candidate models for the dose response relationship will be considered ([APPENDIX 3](#)), but in case of inability to correctly fit data, a model could be removed from the analyses:

- Linear model (no parameters)
- Quadratic model (δ)
- E_{max} model (ED_{50})
- Sigmoidal E_{max} (ED_{50} , h)

Once a set of candidates are identified, the selection will be made using the MCPMod function from DoseFinding R package. The null hypothesis of a constant dose-response curve for the primary endpoint will be tested at the significance level of 5% against the one-sided alternative hypothesis of a non-constant dose response curve using the gMCP-Mod methodology.

For each of the dose-response models in the candidate set, the null hypothesis that the sum of the components of the optimal contrast vector is equal to zero will be tested. To do so, the contrast coefficients of each model are chosen so they maximize the power to detect the absence of dose response.

Under the null hypothesis, the vector of the optimal contrasts for the candidate models follows

Document:

Author:

Version Number:

V2.0

Version Date:

21MAY2020

Template No: CS_TP_BS016 Revision 4
Effective Date: 01Apr2016

Reference: CS_WI_BS005

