Step 5: Fit the primary MMRM model for each penalty and imputation to obtain the estimates at each postbaseline visit.

Suppose the primary MMRM model adopted the unstructured covariance model:

```
ODS OUTPUT DIFFS=CHGDIFF_TIPPING LSMEANS=CHGLSMN_TIPPING;
PROC MIXED DATA=ANALYSIS_PENALTY;
  BY DELTA _IMPUTATION_;
  CLASS SUBJID REGION TRTP WEEK;
  MODEL TOTCFB = TOTBL REGION TRTP WEEK TRTP*WEEK / DDFM=KR;
  REPEATED WEEK / SUB=SUBJID TYPE=UN;
  LSMEANS TRTP*WEEK / PDIFF CL;
RUN;
```

Step 6: Use proc MIANALYZE similar to above to combine the estimates from each imputation for each delta using Rubin's rules. See example for LS Means below.

```
ODS OUTPUT PARAMETERESTIMATES=LSMEST_TIPPING_MIAN;
PROC MIANALYZE DATA = CHGLSMN_TIPPING;
  BY DELTA TRTP WEEK;
  MODELEFFECTS ESTIMATE;
  STDERR STDERR;
RUN;
```

This analysis is repeated for a range of deltas, starting at 0% of the treatment difference at each postbaseline visit, and increasing in increments of 5% until either the tipping point (where the statistical significance of the treatment effect is lost) is identified or the 100% penalty is applied. Tipping point could be reached at different deltas for each SEP-4199 treatment group. Once the tipping point %delta is identified, smaller %delta increments (eg 1%) may be selected for further analysis.

Document:

Author:

Version Number:
Version Date:

V2.0

21MAY2020

Template No: CS_TP_BS016 Revision 4
Effective Date: 01Apr2016

Reference: CS_WI_BS005

MCP-MOD ANALYSIS

The primary efficacy endpoint, change from baseline in MADRS score at Week 6, will also be analyzed using the gMCP-Mod approach for the ITT population. The analysis will be done in two steps.

Step 1: MCP step

The MCP step consists of specifying a set of candidate models for the dose response relationship. First, the following four candidate model families will be selected to describe the potential dose-response curve $f(d, \theta)$.

- Linear model: $f(d, \theta) = E_0 + \delta d$

For the linear model, E_0 is the drug effect at $d \approx 0$ and δ is the slope associated with d . There is no parameter to be estimated for the linear model.

- Quadratic model: $f(d, \theta) = d + \delta d^2$

The quadratic model is intended to capture a possible non-monotonic dose-response relationship. For the quadratic model, there is one parameter δ to be estimated.

- E_{\max} model: $f(d, \theta) = E_0 + E_{\max} d / (ED_{50} + d)$

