The E_{\max} model is used to represent monotone, concave dose-response shapes. To distinguish it from the more general sigmoid E_{\max} model it is sometimes also called hyperbolic E_{\max} model. For the E_{\max} model, there is one parameter ED_{50} to be estimated.

- Sigmoidal E_{\max} : $f(d, \theta) = E_0 + E_{\max} d^h / (ED_{50}^h + d^h)$

The sigmoid E_{\max} model is an extension of the (hyperbolic) E_{\max} model by introducing an additional parameter h , that determines the steepness of the curve at the ED_{50} value. The sigmoid E_{\max} model describes monotonic, sigmoid dose-response relationships. For the Sigmoid E_{\max} model, there are two parameters ED_{50} and h to be estimated.

The next step is to determine the initial values of model parameters for the candidate models. Initial values for standardized model parameters can be calculated based on observed value at Week 6..

```
fitlinear<- fitMod(dose=dose, resp= resp, data = xxx, model="linear")
fitquadratic<- fitMod(dose=dose, resp= resp, data = xxx, model="quadratic")
fitemax<- fitMod(dose=dose, resp=resp, data = xxx, model="emax")
fitsigemax<- fitMod(dose=dose, resp=resp, data = xxx, model="sigEmax")
```

Note: Dose is 0 for placebo, 200 for SEP-4199 200mg/day and 400 for SEP-4199 400mg/day. Resp is the response so change from baseline at Week 6 in MADRS Total Score.

Document:

Author:

Version Number:

V2.0

Version Date:

21MAY2020

Template No: CS_TP_BS016 Revision 4
Effective Date: 01Apr2016

Reference: CS_WI_BS005

Based on an estimate of the dose-response vector and its associate variance/covariance matrix, optimal contrast will be computed for each model to maximize the power to test the null hypothesis of a constant dose-response curve. To obtain this estimate, an MMRM model with factors for treatment dose level, region, week, and baseline MADRS score as a continuous covariate will be used to model the change from baseline in MADRS score over time from the placebo and SEP-4199 groups for the ITT population. This analysis can be performed using the SAS software ([Dmitrienko, 2017](#)).

```

PROC MIXED;
  CLASS SUBJID REGION TRTPN WEEK;
  MODEL TOTCFB = TOTBL REGION TRTPN WEEK TRTP*WEEK / DDFM=KR RESIDUAL;
  REPEATED WEEK/TYPE=UN SUBJECT=SUBJID;
  LSMEANS TRTPN*WEEK /PDIFF CL COV;
  *ODS OUTPUT LSMEANS=MUH (KEEP=TRTPN WEEK ESTIMATE);
  *ODS OUTPUT LSMEANS=COVH (KEEP=TRTPN WEEK COVx COVy COVz) ;
RUN;

```

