where COVx COVy COVz are representing the columns associated to LS Means estimated for Placebo, SEP-4199 200mg/day and 400 for SEP-4199 400mg/day at Week 6.

The vector of the optimal contrast estimates corresponding to the set of candidate models is asymptotically normally distributed. The test statistic used for establishing an overall dose response signal is the maximum t-statistics of the individual model test statistics. Critical values for tests with (asymptotically) exact level α can be derived from the joint distribution of the t statistics, which can be obtained from the joint distribution of the contrast estimates ([Pinheiro 2014](#)). Multiplicity adjusted p-values for the individual model contrast tests can be derived similarly. The mvtnorm package in R includes functions to calculate quantiles and probabilities for the underlying multivariate normal distributions ([Pinheiro 2014](#), [Genz 2009](#)).

The optimal contrasts corresponding to the candidate models are calculated using the optContr function in the DoseFinding package in R ([Pinheiro 2014](#)). Model specific contrast coefficients and contrast correlation matrix will be displayed in R outputs.

```

doses <- c(0, 200, 400)
Delta=coef(fitquadratic)[["b2"]]/abs(coef(fitquadratic)[["b1"]])

mod <- Mods(emax = coef(fitemax)[["ed50"]],
            quadratic = Delta,
            sigEmax = coef(fitsigemax)[c("ed50","h")],
            linear = NULL,
            doses = doses, direction = "decreasing")
plot(mod, xlab= "Doses" , ylab= "Model Means" )

contMat <- optContr(mod, S=covH)
summary(contMat)
plot(contMat, xlab= "Doses" , ylab= "Optimal Contrasts" )

```

Document:

Author:

Version Number:
Version Date:

V2.0
21MAY2020

Template No: CS_TP_BS016 Revision 4
Effective Date: 01Apr2016

Reference: CS_WI_BS005

The optimal model contrast tests will be performed using the MCTtest function in the DoseFinding package in R, based on the multiple comparison approach described above (Pinheiro 2014).

```
MCTtest(doses, muH, S=covH, type = "general", critV = TRUE, pVal = TRUE, alpha=0.05, alternative='one.sided', contMat=contMat)
```

Step 2: Mod step

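### The MCP-Mod contrasts are built from the same Week 6 data they test, so the stated one-sided 5% level is not guaranteed (about 4.5% to 10%)

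*SAP*

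**What the plan says.** SAP section 16.1.5.3 describes a supplementary generalized MCP-Mod analysis of the Week 6 MADRS change with four candidates: linear, quadratic, Emax and sigmoid Emax. The flat-curve null "will be tested at the significance level of 5% against the one-sided alternative hypothesis of a non-constant dose response curve". Rejection is said to demonstrate proof of concept. A candidate may also be dropped: "in case of inability to correctly fit data, a model could be removed from the analyses".

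Appendix 3 (MCP-MOD ANALYSIS, Step 1) says where the shapes come from: "Initial values for standardized model parameters can be calculated based on observed value at Week 6". The code fits each model to the trial's Week 6 change from baseline. It puts the fitted ED50, the fitted ED50 and h, and the fitted b2/|b1| into `Mods()`, with the direction set to decreasing, and then runs "contMat <- optContr(mod, S=covH". The contrast matrix goes to `MCTtest()` at alpha 0.05, one-sided, together with the MMRM least-squares means at Week 6. The text relies on "Critical values for tests with (asymptotically) exact level" alpha. Neither document gives a numeric ED50, h or quadratic coefficient.

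If no contrast is significant, section 16.1.5.3 ends the exploration. For that same case, Appendix 3 Step 2 supplies code that fits all four models and returns gAIC, coefficients and plots.

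**The concern.** Appendix 3 calls the fitted quantities initial values, but in the code they are the candidate shapes themselves. The contrasts are therefore random and correlated with the means they test, while the critical value is computed as if they had been chosen beforehand. A contrast that bends toward the observed means can give a larger maximum statistic than its reference distribution allows.

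Two features make the level harder to pin down. The SAP says "The quadratic model is intended to capture a possible non-monotonic dose-response relationship" and prints it as d + delta·d², yet the code divides by |b1| and asks for a decreasing direction. How the sign is then handled is left to the package ("generalized MCP-Mod using the DoseFinding package, version 0.9-16"). Sigmoid Emax also has four parameters (E0, Emax, ED50, h) for three dose means, so ED50 and h cannot both be determined, and bounds or starting values would influence its contrast. The SAP specifies neither.

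At stake is how the result is read. A rejection at a nominal 5% is described as proof of concept, and it opens the minimum-effective-dose estimation.

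**Working it through.** **Inputs from the documents.** Doses 0, 200 and 400 mg; 1:1:1 allocation; one-sided alpha 0.05; four candidate models; shapes fitted to the Week 6 change (SAP 3.2, 16.1.5.3, Appendix 3).

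**Assumptions not in the documents.** Known equal variances; ED50 between 0.4 and 600 mg; h between 0.5 and 10; and three treatments of the quadratic, with Delta = b2/|b1|:
- A: −d + Delta·d² (only the linear part reversed)
- B: −(d + Delta·d²) (the whole curve reversed)
- C: quadratic removed

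**Method.** Under a flat null, the three standardized means, after removing their average, form a two-dimensional standard normal vector of length R and direction φ, with φ uniform on the circle. Each shape becomes a unit contrast u. Fitted shapes depend only on φ. Let m(φ) be the largest inner product between a contrast and direction φ, and q(φ) the 5% critical value computed as if those contrasts were fixed. When the fitted and tested means are identical:

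P(reject | φ) = P(R·m > q) = exp(−q² / (2m²)) for m > 0, and the level is the average over φ.

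This does not depend on the sample size or the SD.

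**Reproducing the stated 5%.** With one illustrative set of shapes fixed in advance, the critical value is 1.787 and the level is 5.00%. The SAP's primary power (section 3.4) was also recovered: with 93 per arm, effect size 0.44 and truncated Hochberg with gamma 0.9, it is 90.5% for at least one rejection and 75.2% for both, against about 90% and 75% stated.

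**A hand check of treatment A.** Whenever the fitted b1 is negative, which is half of all directions, the quadratic candidate has exactly the observed shape, so m = 1. With all four models, q ranges from 1.6993 to 2.1193. Even at the largest q, exp(−2.1193²/2) = 0.106, and half of that is 5.3%. Those directions alone use more than the nominal level. At the smallest q, exp(−1.6993²/2) = 0.236, and half is 11.8%. The full integral should fall near or within that interval, and it does.

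**Why treatment B is milder.** When b1 is negative, the candidate has the observed curvature reversed. When b1 is positive, it is the exact negative of the observed shape. The quadratic then mostly raises q and seldom produces a rejection.

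**Results: true one-sided level at nominal 5%.**

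| Quadratic | Sigmoid Emax | Identical means | Correlation 0.95 to 0.80 |
|---|---|---|---|
| A | kept | 10.2% | 9.8% to 8.9% |
| A | dropped | 10.0% | 9.6% to 8.7% |
| B | kept | 5.5% | 5.4% to 5.2% |
| B | dropped | 4.7% | 4.6% to 4.5% |
| C | kept | 6.8% | 6.7% to 6.3% |
| C | dropped | 5.8% | 5.8% to 5.6% |

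The last column allows for the shapes being fitted to observed changes while the test uses MMRM means. The correlations are an assumed range, evaluated by simulation.

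Sigmoid Emax adds 10.2 − 10.0 = 0.2 points under A, 5.5 − 4.7 = 0.8 under B and 6.8 − 5.8 = 1.0 under C. Under B it accounts for the whole excess over 5%.

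**Sensitivity to bounds.** With ED50 4 to 400 and h 1 to 5, identical means, the levels with (without) sigmoid Emax are 10.0% (9.8%) for A, 5.4% (4.6%) for B and 6.6% (5.7%) for C. Widening only the Emax ED50 range to 0.4 to 4,000 gives 10.6% (10.3%) for A and 5.6% (4.8%) for B. A less likely set, linear plus quadratic only, gives 10.6% under A and 3.7% under B.

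**The case against.** The strongest reply is that the documents settle neither the size nor the direction of the error. The range straddles 5%, and under treatment B without sigmoid Emax the test is slightly conservative. The doubling depends on a package convention that was not available to check, and the parameter bounds and correlations are assumed. That stands, and the conclusion is accordingly that the level is not guaranteed, not that it is doubled. Treatment C needs no sign assumption, however, and exceeds 5% in every case calculated.

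A second reply is that the analysis is already called supplementary and exploratory, lies outside the H1 to H4 gatekeeping, and does not determine study success. This is true and limits the priority. It does not remove the 5% level, the exact-level statement or the proof-of-concept wording.

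Third, the clause allowing a model to be removed could deal with an unidentifiable sigmoid Emax. It does so only after the data are seen, and the choice itself moves the level.

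Fourth, the non-significant branch of the code may be meant only as descriptive output, since section 16.1.5.3 also promises a table of AIC for each model and the branch yields no target dose. That is a fair reading, so this part is minor. The text still says the exploration stops, and the two places need to agree.

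**Conclusion.** The concern holds. As written, the contrasts come from the data they test, and the one-sided 5% level and the claim of asymptotically exact critical values do not follow. The true level is approximately 4.5% to 10%, depending on the quadratic sign convention and on which models are kept; unusual model sets fall slightly outside that range. These figures rest on equal known variances, the assumed ED50 and h bounds, and identical or strongly correlated fitted and tested means. Estimating both ED50 and h from three dose means is not possible without outside constraints. The conflict between section 16.1.5.3 and Appendix 3 Step 2 is real but minor.

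Type I error control for the primary and secondary hypotheses is unaffected. This should be corrected, at low to moderate priority.

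**What to change.** Before unblinding:

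- Write numeric candidate parameters and the quadratic sign convention into the SAP, and compute the contrasts from those values.
- Failing that, remove the 5%, exact-level and proof-of-concept statements and label the test itself exploratory.
- Do not estimate both ED50 and h of sigmoid Emax from three dose means.
- Make section 16.1.5.3 and the non-significant branch in Appendix 3 Step 2 agree, for example by stating that the branch is descriptive only.

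The cost is SAP text and R code edits, plus some possible loss of power. With two illustrative fixed sets (not recommendations), 93 per arm and the SAP Appendix 4 effect sizes, power under Scenario 1 (0.44/0.44) is 95.0% to 95.7%, against 95.8% to 96.5% with data-derived shapes. Under Scenario 2 (0.22/0.44) it is 88.7% to 89.6%, against 90.6% to 92.4%. Part of that gap reflects the higher true level of the data-derived test.

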APPENDIX 4. SAMPLE SIZE: POWER CALCULATION

The optimal value of the truncation parameter is chosen to maximize an appropriate power function. For this study, definition 1, the probability to reject at least one truly significant comparison for endpoint E1 in Family 1 was considered as the primary. In addition, the following power functions were also investigated:

- Definition 2: Probability of rejecting at least one truly significant comparison for endpoint E2 (Family 2)
- Definition 3: Probability of rejecting at least one truly significant comparison among all 4 comparisons for endpoint E1 and endpoint E2 in Family 1 and Family 2
- Definition 4: Probability of rejecting both truly significant comparisons for endpoint E1 (Family 1)
- Definition 5: Probability of rejecting both truly significant comparisons for endpoint E2 (Family 2)
- Definition 6: Probability of rejecting all four truly significant comparisons for endpoint E1 and endpoint E2 in Family 1 and Family 2
- Definition 7: Probability of rejecting at least one truly significant comparison for endpoint E1 (Family 1) and at least one truly significant comparison for endpoint E2 (Family 2)
- Definition 8: Probability of rejecting both truly significant comparisons for endpoint E1 (Family 1) and at least one truly significant comparison for endpoint E2 (Family 2)
- Definition 9: Probability of rejecting H_2 (400 mg/day versus Placebo in Family 1) and H_4 (400 mg/day versus Placebo in Family 2)
- Definition 10: Probability of rejecting H_1 (200 mg/day versus Placebo in Family 1) and H_3 (200 mg/day versus Placebo in Family 1).

Table 6 below shows two scenarios considered for effect size assumptions.

Table 6. True effect sizes used in the power assessment

	200 mg/day vs Placebo	400 mg/day vs Placebo
Scenario 1		
Family 1 (Endpoint E1)	0.44	0.44
Family 2 (Endpoint E2)	0.38	0.38
Scenario 2		
Family 1 (Endpoint E1)	0.22 (half the 400 mg/day dose)	0.44

Document:

Author:

Version Number:

V2.0

Version Date:

21MAY2020

Template No: CS_TP_BS016 Revision 4
 Effective Date: 01Apr2016

Reference: CS_WI_BS005

Family 2 (Endpoint E2)	0.19 (half the 400 mg/day dose)	0.38
------------------------	---------------------------------	------

Table 7 shows the correlation assumption between the 2 endpoints within a treatment.

Table 7. Correlation assumption used in the power assessment

	Endpoint 1	Endpoint 2
Endpoint 1	1	0.8
Endpoint 2	0.8	1

Table 8 and Table 9 below show the power calculations based on 93 subjects/group sample size for a range of gamma, γ , parameters for scenario 1 and scenario 2, respectively based on 10,000 simulation runs with a 1-sided 0.025 alpha level. The larger the value of γ , the higher the power of the Family 1 test and the lower the power of the Family 2 test. In the extreme case, when the truncation parameter is set to 1, the power of the Family 1 test will be maximized (the hypotheses in Family 1 would be tested using the regular Hochberg test) and the power of the Family 2 test would be minimized (it would be reduced to 0 and it would be impossible to reject any hypotheses in Family 2 unless all hypotheses in Family 1 are rejected). On the other hand, if the truncation parameter is set to 0, the power of the Family 1 test would be minimized (the truncated Hochberg test would be reduced to the Bonferroni test) but the power of the Family 2 test would be maximized.

Table 8. Power simulations for Scenario 1

Gamma	Defn 1	Defn 2	Defn 3	Defn 4	Defn 5	Defn 6	Defn 7	Defn 8	Defn 9	Defn 10
0	0.8939	0.7645	0.8939	0.6538	0.5221	0.5221	0.7645	0.6048	0.6409	0.6457
0.1	0.8939	0.7606	0.8939	0.6677	0.5296	0.5296	0.7606	0.6164	0.6434	0.6468
0.2	0.8942	0.7578	0.8942	0.6816	0.5357	0.5357	0.7578	0.6274	0.6448	0.6487
0.3	0.8950	0.7549	0.8950	0.6939	0.5415	0.5415	0.7549	0.6370	0.6456	0.6508
0.4	0.8964	0.7513	0.8964	0.7041	0.5453	0.5453	0.7513	0.6443	0.6466	0.6500
0.5	0.8980	0.7469	0.8980	0.7152	0.5492	0.5492	0.7469	0.6518	0.6452	0.6509
0.6	0.8992	0.7411	0.8992	0.7247	0.5526	0.5526	0.7411	0.6585	0.6441	0.6496
0.7	0.9004	0.7338	0.9004	0.7341	0.5559	0.5559	0.7338	0.6652	0.6424	0.6473
0.8	0.9016	0.7265	0.9016	0.7426	0.5592	0.5592	0.7265	0.6713	0.6402	0.6455
0.9	0.9027	0.7173	0.9027	0.7517	0.5633	0.5633	0.7173	0.6782	0.6391	0.6415
1	0.9034	0.6847	0.9034	0.7605	0.5663	0.5663	0.6847	0.6847	0.6236	0.6274

The following definitions are the same by definition: defn1=defn 3, Defn2=defn7, Defn5=defn6.

Table 9. Power simulations for Scenario 2

Gamma	Defn 1	Defn 2	Defn 3	Defn 4	Defn 5	Defn 6	Defn 7	Defn 8	Defn 9	Defn 10
0	0.7856	0.6124	0.7856	0.2143	0.1445	0.1445	0.6124	0.1962	0.6002	0.1567
0.1	0.7859	0.6029	0.7859	0.2273	0.1502	0.1502	0.6029	0.2061	0.5912	0.1619
0.2	0.7858	0.5892	0.7858	0.2344	0.1536	0.1536	0.5892	0.2118	0.5780	0.1648
0.3	0.7863	0.5810	0.7863	0.2476	0.1581	0.1581	0.5810	0.2226	0.5706	0.1685
0.4	0.7868	0.5687	0.7868	0.2554	0.1604	0.1604	0.5687	0.2280	0.5586	0.1686
0.5	0.7871	0.5525	0.7871	0.2630	0.1631	0.1631	0.5525	0.2341	0.5426	0.1730
0.6	0.7875	0.5347	0.7875	0.2726	0.1666	0.1666	0.5347	0.2417	0.5254	0.1759
0.7	0.7877	0.5135	0.7877	0.2811	0.1692	0.1692	0.5135	0.2483	0.5045	0.1782
0.8	0.7879	0.4830	0.7879	0.2904	0.1728	0.1728	0.4830	0.2563	0.4746	0.1812
0.9	0.7885	0.4339	0.7885	0.2996	0.1760	0.1760	0.4339	0.2633	0.4263	0.1836

Document:

Author:

Version Number:

V2.0

Version Date:

21MAY2020

Template No: CS_TP_BS016 Revision 4
 Effective Date: 01Apr2016

Reference: CS_WI_BS005

1	0.7890	0.2709	0.7890	0.3092	0.1788	0.1788	0.2709	0.2709	0.2637	0.1860
---	--------	--------	--------	--------	--------	--------	--------	--------	--------	--------

The following definitions are the same by definition: defn1=defn 3, Defn2=defn7, Defn5=defn6.

Type I error rate assessment:

Table 10 displays the Type I error rate (probability of rejecting at least one null hypothesis out the four null hypotheses) for various values of γ assuming a zero effect size for both endpoints and a correlation of 0.8 between endpoints based on 10,000 simulation runs.

Table 10. Type 1 error rate: probability of rejecting at least one null hypothesis out of 4 comparisons

Gamma	Zero effect size
0	0.0237
0.1	0.0237
0.2	0.0237
0.3	0.0237
0.4	0.0239
0.5	0.0239
0.6	0.0240
0.7	0.0240
0.8	0.0240
0.9	0.0240
1	0.0242

Document:

Author:

Version Number:

V2.0

Version Date:

21MAY2020

Template No: CS_TP_BS016 Revision 4
 Effective Date: 01Apr2016

Reference: CS_WI_BS005

